#### *Sensitivity analyses*

In our primary analysis death is treated as a competing risk for recovery (i.e., someone that dies will never recover) by censoring subjects at their date of death. Although we anticipate low mortality rates (e.g., 1.4%) censoring patients due to death has the potential to bias recovery rate estimates. In order to assess this assumption we will explore the use of a more complex approach that explicitly models the subdistribution of recovery rate. If results from this analysis are substantially different from the primary analysis, then we will use model fit statistics and Monte Carlo simulation to determine whether the more complex model better describes the data generating process.

#### *Secondary and exploratory endpoint analyses*

Secondary endpoints include time to resolution of fever, time to improvement of symptoms, duration of hospitalization, proportion requiring supplementary oxygen above baseline usage, duration of requirement for supplementary oxygen, proportion requiring ICU admission, proportion requiring mechanical ventilation, ventilator free days, all-cause mortality. Exploratory COVID-19 specific mortality, number of patients with diagnosed cardiomyopathy, number of patients with new onset arrhythmia. All secondary and exploratory endpoints will be analyzed by survival analysis (KM and/or Cox), t-tests, chi-square tests, or Fisher's exact tests as appropriate.

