### **Secondary**

1. Time to resolution of fever defined as at least 48 hours since last temperature  $\geq 38.0^{\circ}\text{C}$  without the use of fever-reducing medications

2. Time to improvement in symptoms (scored as mild or absent and remained so for 24 hour)
3. Mean improvement in symptom from baseline
4. Duration of hospitalization
5. Proportion requiring supplementary oxygen (above baseline usage) at any time during follow-up
6. Duration (days) of requirement for supplementary oxygen
7. Proportion requiring ICU admission at any time during follow-up
8. Proportion requiring mechanical ventilation at any time during follow-up
9. Ventilator free days
10. All-cause mortality

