### Follow up

Participants will be asked to complete daily symptom surveys for 14 days from randomization, then weekly thereafter for 4 weeks resulting in a total duration of follow up of 42 days. During hospitalization, daily symptom surveys will be completed in conjunction with the study coordinators via telephone. On discharge participants will have the option to complete electronic symptom surveys or complete symptom surveys via telephone with study coordinator. In the event that the participant opts for electronic symptom surveys on discharge they will also

receive a follow up call from a study coordinator every 7 days during the initial 14 day period. In addition, failure to submit a symptom survey will prompt a study follow up call.

On discharge from hospital in addition to completing daily symptom surveys participants will be asked to take and record their temperature twice daily with extra recordings performed if concern for fever onset.

Symptoms will be collected using the Flu-PRO scale (appendix 1) validated for use in influenza as at present validated tools for COVID-19 are not available.

To assure safety and protocol adherence phone calls to participants will be initiated if there is no contact at the designated time points.

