#### *Primary endpoint analysis*

The primary endpoint of this study is the time to recovery following the definition outlined in the STUDY AIMS/ENDPOINTS section. Our primary analysis will be to use Kaplan-Meier (KM) survival analysis to test the statistical null hypothesis that there is no difference in recovery rates between the non-AZM treatment arms and the AZM treatment arms (HCQ vs HCQ + AZM, CQ vs CQ + AZM). If either of the AZM arms have significantly faster recovery rates (two-sided  $P$ -value  $< 0.05$ ) compared to the corresponding non-AZM arm group, then we will conclude that the AZM group is superior to the non-AZM group. We will also compare recovery rates between the HCQ vs CQ, and HCQ + AZM vs CQ + AZM treatment arms to assess whether HCQ and CQ treatments differentially influence recovery. We will then proceed to a multivariable Cox-regression model that adjusts symptom severity at baseline (sum of presence of fever  $\geq 38.0^{\circ}\text{C}$  and total number of 'Quite a Bit' or 'Very much' responses to the Flu-PRO questionnaire [maximum total = 20]). The final model will retain the treatment groups and those covariates that are significant ( $P < 0.05$ ) in the multivariable model and we will report the model-adjusted hazard ratios and 95% CI for the treatment groups as well as the covariates. Participants that are lost to follow-up or die will be censored at the date of last contact or date of death, respectively, and patients that do not recover during the study period will be censored at 42 days. The primary analysis will be intention-to-treat and a per-protocol analysis will also be performed as a secondary analysis of the primary endpoint. Statistical analyses will be conducted using PROC LIFETEST and PROC PHREG as appropriate (SAS Institute Inc, Cary, NC, USA).

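### Secondary endpoint 3 (mean symptom improvement) is not named in the analysis section, has no defined score or day, and is offered only an unadjusted t-test where baseline adjustment would be more precise

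*Combined protocol and SAP*

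**What the plan says.** The Secondary lists in the Protocol Summary and in Study Aims/Endpoints each hold ten items. Item 3 reads, in full, "Mean improvement in symptom from baseline". Neither list gives a score, a day or a summary measure for it.

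The section Secondary and exploratory endpoint analyses opens its list with "Secondary endpoints include time to resolution of fever, time to improvement of symptoms, duration of hospitalization". It moves from item 2 straight to item 4 and names nine of the ten. It then closes: "All secondary and exploratory endpoints will be analyzed by survival analysis (KM and/or Cox), t-tests, chi-square tests, or Fisher's exact tests as appropriate".

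Under Follow up, "Participants will be asked to complete daily symptom surveys for 14 days from randomization, then weekly thereafter for 4 weeks". The instrument is given in the same section: "Symptoms will be collected using the Flu-PRO scale (appendix 1) validated for use in influenza". The Schedule of events adds a symptom screen at Day 0. Appendix 1 prints five verbal response categories with no numeric codes.

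Baseline symptom severity is used as a covariate in one place only, under Primary endpoint analysis: a "multivariable Cox-regression model that adjusts symptom severity at baseline". The severity count defined there is not linked to endpoint 3.

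**The concern.** Three gaps meet in one endpoint.

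- **It is not named where its analysis should be specified.** It falls under the catch-all sentence and nothing else.
- **Its content is open.** With no score and no day, many different analyses would all count as endpoint 3. Treatment is open-label, participants rate their own symptoms, and coordinators who help with the surveys know the arm. Unless the day is fixed in advance, nobody can later show that it was chosen without sight of the results.
- **The methods on offer leave precision unused.** Endpoint 3 is a mean change from baseline. The only listed method that compares means is the t-test, and no baseline-adjusted method is offered for any continuous outcome, although a Day 0 assessment is scheduled and the sponsor already adjusts for baseline severity in the primary Cox model.

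At stake are wider confidence limits than the same data allow, a result that moves with chance baseline imbalance, and a reported p-value that may reflect the choice of day.

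**Working it through.** **The plan's own figure.** The documents give no figure for endpoint 3. The only power figure is for the primary endpoint (Sample size and power analysis): medians 11 and 7 days, censoring 0.04 per day, 125 per arm, two-sided alpha 0.05, stated power 82%. With exponential hazards:

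- hazards ln2/11 = 0.0630 and ln2/7 = 0.0990; ratio 11/7 = 1.571
- P(recovery by day 42) = h/(h + 0.04) × [1 − exp(−42(h + 0.04))] = 0.604 and 0.710
- events = 125 × (0.604 + 0.710) ≈ 164
- power = Φ(√164 / 2 × ln 1.571 − 1.96) ≈ 82.5%

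The stated 82% reproduces and does not involve endpoint 3.

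**Counts.** Declared secondary endpoints: 10. Named in the analysis section: 9, with only item 3 missing. Post-baseline surveys: 14 daily + 4 weekly = 18 (days 1 to 14, 21, 28, 35, 42), or 19 with Day 0.

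**Precision.** Let s be the SD of the score at both times and r the baseline-to-follow-up correlation. The documents give neither, so r is assumed and shown over a range.

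- Per-patient variance, change score: 2(1 − r)s²
- Per-patient variance, ANCOVA: (1 − r²)s²
- Ratio, ANCOVA to change score: (1 + r)/2
- Detectable difference, 125 against 125 with complete data, 80% power, two-sided 0.05: (1.960 + 0.842) × √(2/125) = 0.3544 times the method's SD

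| Assumed r | Variance ratio | SE reduction | Detectable difference, change / ANCOVA (in s) | Power for an assumed 0.3 s difference, change / ANCOVA |
|---|---|---|---|---|
| 0.2 | 0.60 | 22.5% | 0.448 / 0.347 | 46.6% / 67.7% |
| 0.4 | 0.70 | 16.3% | 0.388 / 0.325 | 58.1% / 73.5% |
| 0.6 | 0.80 | 10.6% | 0.317 / 0.284 | 75.5% / 84.2% |

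Expressed as sample size, the change score needs 1/0.60 = 1.67 to 1/0.80 = 1.25 times as many patients for the same precision.

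The direction does not depend on equal SDs. With baseline SD s0 and follow-up SD s1, the change-score variance minus the ANCOVA variance is (s0² + s1² − 2r·s0·s1) − s1²(1 − r²) = (s0 − r·s1)², which is never negative. If spread narrows as symptoms resolve, the gain grows. At s1/s0 = 0.7 and r = 0.4 the ratio is 0.49 × 0.84 / (1 + 0.49 − 0.56) = 0.412/0.93 = 0.44.

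**Free choice of day.** Under no treatment effect, the chance that at least one of the 18 days gives p < 0.05 is:

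- independent days (an upper reference only): 1 − 0.95^18 = 60%
- test statistics with an assumed AR(1) day-to-day correlation of 0.80, 0.90 or 0.95 (200,000 simulated sets each): 45%, 36% or 27%
- one day named in advance: 5%

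**The case against.** The strongest reply is that this is mostly missing detail. The closing sentence of the analysis section reaches all secondary endpoints, item 3 is declared twice, and a list introduced with a word such as include need not be complete. That stands. A reader might infer that the endpoint has been dropped from the trial, but the text does not support it.

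A reader might also infer that a t-test on change is the stated plan. It is not. The section gives a menu, to be used as appropriate, and assigns nothing to endpoint 3. The t-test is an inference, though a fair one: nothing else on the menu compares means, and nothing on it adjusts a continuous outcome for baseline.

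A third tempting reading is that the result would be biased. With randomised arms, a change-score t-test is unbiased and keeps its type I error when the day and score are fixed. The cost is precision, and sensitivity to whatever baseline imbalance happens to arise.

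It is also fair to say that r is not in the documents, so 11% to 23% is a range under assumption and not a measured property of this trial. Likewise, the selection figures rest on assumed correlations and allege no intent.

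Finally, baseline adjustment does not deal with missing scores. If the planning rate of 0.04 per day for death or loss held constantly, 1 − exp(−0.04 × 14) = 43% would be gone by day 14. That could matter more for a mean score than the gain in standard error, so the remedy has to cover it.

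**Conclusion.** The point holds as a specification gap with a better method at hand. Endpoint 3 is not named in the analysis section and lacks a score and a day. Where a mean is to be compared, the plan offers only an unadjusted t-test.

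Baseline adjustment would cut the standard error by about 23% to 11% for an assumed r of 0.2 to 0.6 with equal SDs. It never does worse in large samples, whatever the SDs. The open choice among 18 surveys in an open-label trial is at least as important, because it cannot be repaired once results have been seen.

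The reach is limited to one of ten secondary endpoints. The superiority conclusion rests on time to recovery, and the 82% power is untouched. A reader might take this as a threat to the trial's main result; the documents give no ground for that.

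**What to change.** In Secondary and exploratory endpoint analyses:

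1. Name endpoint 3 in the list.
2. Define one Flu-PRO summary score: which items enter, how the five response categories are coded, and how an incomplete questionnaire is scored.
3. Pre-specify a single estimand: either the between-arm difference in the score at one named day within days 1 to 14, or one repeated-measures contrast over days 1 to 14. These are different quantities, so choose one, not both.
4. Replace the t-test for this endpoint by ANCOVA (single day) or a mixed model (repeated measures), with the Day 0 score as covariate in either case.
5. State how deaths and missing surveys are handled. A mixed model under missing-at-random does not by itself settle what the score means for a patient who has died.

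No new data are needed: the Day 0 screen and the daily surveys are already scheduled. Items 1 to 4 cost only wording. Item 5 needs a real decision and probably one sensitivity analysis. All five should be settled before anyone looks at symptom data by arm.

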#### **Sample size and power analysis**

Version 2.0. March 30th 2020

Page 18 of 18

A recent COVID-19 study in the Jiangsu province of China indicated that fever in about half of COVID-19 infected people lasted less than 7 days. Because this research area is rapidly developing and there is limited knowledge about this disease, we use the simple median estimate of 7-days as a starting point for our recovery outcome. In addition to attenuation of fever, our primary outcome adds criteria that fever must be attenuated for at least 48 hours and there needs to be symptom improvement. Given our criteria we assume 11 days as a rough estimate for median recovery time in the non-AZM treatment groups to compare the AZM treatment groups against in our study. This study is powered to test the hypothesis that HCQ + AZM improves recovery rate compared to HCQ alone, and CQ + AZM improves recovery rate compared to CQ alone. Assuming a minimum improvement of 4 days in the median recovery time (median recovery time of 7-days) and a censoring rate due to death or loss to follow-up of 0.04 per day, we plan on enrolling a total of 500 participants (125 per arm) which would give us just over 80 percent power ( $1 - \beta = 82\%$ ,  $\alpha = 0.05$ ) to test our primary hypotheses.

## **SOURCE DOCUMENTATION**

All source documents will be kept in an appropriately secure office in a locked high density filing system in a locked office.

## **QUALITY CONTROL**

All eligibilities and ICFs and a portion of the study case report forms (no less than 10%) will be audited by the study quality management personnel.

## **ETHICS AND PROTECTION OF HUMAN SUBJECTS**

Once the study is approved by the Washington University Human Research Protection Office (HRPO), recruiting and screening will begin for the study. All subjects or their legally authorized representative (LAR) are required to read English, understand and sign the informed consent document.

## **DATA HANDLING AND RECORD KEEPING**

Data will be generated and managed according to Washington University School of Medicine and HIPAA policy.

Data will be entered onto a central Redcap database housed at Washington University. All research records will be maintained under the two-lock rule with access limited to authorized study personnel or regulatory authorities. The study records will be maintained up to seven years after the completion of the study.

## **PUBLICATION POLICY**

The PI and co-investigators will participate in manuscript preparation and submission to journals.

**Appendix 1 Flu-PRO questionnaire (Will be modified to read COVID-19 where Flu/influenza referenced)**

Participant ID: \_\_\_\_\_ Participant Initials: \_\_\_\_\_ Date: \_\_\_\_ / \_\_\_\_ / \_\_\_\_

**Influenza Symptoms Questionnaire**

People experience ~~the Flu~~ COVID-19 in different ways. We would like to know about the symptoms you have been experiencing during the last 24 hours. For each symptom, please mark one box under the response that best matches your experience. Mark the "Not at all" box, if you did not have that symptom in the past 24 hours.

What time is it? \_\_\_\_ AMP / PM (please circle)

Please rate the extent which you had each symptom during the past 24 hours.

Symptom	Not at all	A little bit	Somewhat	Quite a bit	Very much
Runny or dripping nose					
Congested or stuffy nose					
Scratchy or itchy throat					
Difficulty swallowing					
Teary or watery eyes					
Sore or painful eyes					
Eyes sensitive to light					
Trouble breathing					
Chest congestion					
Chest tightness					
Dry or hacking cough					
Wet or loose cough					
Headache					
Head congestion					
Sinus pressure					
Felt dizzy					
Felt lightheaded					

**Appendix 2 Contraindicated\* with study drugs (predominantly chloroquine)**

Version 2.0. March 30th 2020

Page 21 of 18

Type	Medication
Analgesic	methadone
Antiarrhythmic	amiodarone, digoxin, disopyramide, dofetilide ( Tikosyn ), dronedarone ( Multaq ), flecainide, ibutilide ( Corvert ), procainamide, quinidine, sotalol
Antibiotic	bedaquiline, clarithromycin, delamanid, rifampin
Anticonvulsant	carbamazepine, phenytoin
Antidepressant	bupropion, fluoxetine, paroxetine
Antifungal	itraconazole, ketoconazole, posaconazole, voriconazole
Antihormone therapy	abiraterone, apalutamide, enzalutamide,
Antimalarial	artemether/lumefantrine, dapsone, quinine, mefloquine
Antineoplastic	ceritinib ( Zykadia ), dabrafenib ( Tafinlar ), idelalisib, ivosidenib ( Tibsovo ), lenvatinib ( Lenvima ), mitotane, vandetanib ( Caprelsa )
Antipsychotic	chlorpromazine, ziprasidone
Antiviral	cobicistat, darunavir, lopinavir, nelfinavir, ritonavir, saquinavir, tipranavir
Immunosuppressant	CycloSPORINE
Misc. injection/intravenous	agalsidase $\alpha$ or $\beta$ , conivaptan

\*Includes interactions severe enough to require constant monitoring during co-administration  
(Category D)
